3.6. End of Study

The end of this study is defined as 30 days after the last subject's final study visit in the OLE.

3.7. Biomarker Testing

Samples for biomarker research will be stored for up to 15 years after the end of the study. These analyses are exploratory and individual subject results will not be provided to the study subjects or to the investigators. Because biomarker science is a rapidly evolving area of investigation, it is

not possible to specify prospectively all tests that will be done on the specimens provided. The collection and analysis of research specimens may facilitate the rational design of new pharmaceutical agents and the development of diagnostic tests, which may allow for individualized drug therapy for subjects in the future.

3.7.1. Biomarker Samples to Address the Study Objectives:

Blood will be collected in this study and will be used to evaluate the association of biomarkers with the safety and clinical response to GS-5745 and to increase the knowledge and understanding of the biology of RA and/or autoimmune and related inflammatory diseases. The samples collected can be used for the validation of diagnostics. The specific analyses will include, but are not be limited to, MMP9 levels and activity in blood, as well as pathways relevant to TNF signaling. The testing of MMP9 and markers related to MMP9 pathway, inflammation, autoimmunity, and TNF pathways is based upon the current state of scientific knowledge. The plan may be modified during or after the end of the study to remove tests no longer indicated and/or to add new tests based upon the growing state of art knowledge.

In addition to the study-specific informed consent to be signed by each subject, a separate, specific signature will be required to document a subject's agreement to allow the use of the remainder of their already collected biomarker and PK specimens for optional future research. The specimens retained for optional future research will be used to increase our knowledge and understanding of the biology of the study disease and related diseases and to study the association of biomarkers with disease pathogenesis, progression and/or treatment outcomes, including efficacy, AEs, and the processes of drug absorption and disposition. These specimens may be used also to develop biomarker or diagnostic assays and establish the performance characteristics of these assays.

3.7.2. Biomarker Samples for Optional Genomic Research

PPD

4. SUBJECT POPULATION

4.1. Number of Subjects and Subject Selection

Approximately 75 subjects with moderately to severely active RA who are currently treated with a TNF-inhibitor and MTX for at least 12 weeks will be enrolled in the study.

4.2. Inclusion Criteria

Subjects must meet all of the following inclusion criteria to be eligible for participation in this study.

- 1) Must have the ability to understand and sign a written informed consent form, which must be obtained prior to initiation of the study procedures; subjects who need a representative/guardian to provide consent are not permitted in this study
- 2) Male or female subjects between 18 and 80 years of age inclusive, at time of signing initial informed consent
- 3) Diagnosis of RA according to the 2010 ACR/EULAR classification criteria (See [Appendix 8](#)), confirmed at Screening
- 4) Subjects must meet Class I, II, or III of the ACR 1991 Revised Criteria for Global Functional Status in RA ([Appendix 6](#)), at Screening
- 5) Must have taken oral or parenteral methotrexate (MTX) dosed from 7.5 to 25 mg/week continuously for at least 12 weeks and tolerated this medication, with at least 6 weeks of stable dose (defined as no change in prescription) prior to the first dose of study drug
 - Subjects on MTX may also be on concurrent chloroquine or hydroxychloroquine at a stable dose (defined as no change in prescription) for at least 4 weeks prior to Baseline: if so, they should plan to continue this medication for the duration of the study
 - Must be receiving folic or folinic acid supplementation at Day 1 and throughout the duration of the study, dosed as per investigator
- 6) Must have \geq 12 weeks of **ongoing** treatment with an approved, SC formulation of TNF inhibitor (adalimumab, certolizumab, etanercept, or golimumab, or marketed biosimilar TNF inhibitor), with at least 6 weeks of stable dose (defined as no change in prescription) defined as:
 - Must have a DAS28(CRP) $>$ 3.2 at Screening

AND

- Must have \geq 3 swollen joints and \geq 3 tender joints among 28 joints assessed (using DAS28) at Screening and at Baseline (need not be the same joints)

- 7) Subjects who have previously received other biologic DMARDs for the treatment of RA are eligible, providing the following washout periods for these have been met:
 - Rituximab – none for at least 6 months prior to Baseline and subject has a CD19+ B cell count in normal range (per central lab) at Screening
 - Infliximab – none for at least 8 weeks prior to Baseline
 - Tocilizumab – none for at least 8 weeks prior to Baseline
- 8) Non-steroidal anti-inflammatory drugs (NSAIDs) and/or oral corticosteroids (≤ 10 mg prednisone/day or equivalent) at a stable dose (defined as no change in prescription) for ≥ 4 weeks prior to Baseline are allowed and should be continued at the same stable dose throughout the blinded period of the study; PRN NSAIDs for indications other than RA are also allowed.
- 9) TB Screening: Subjects must meet either a. or b.:
 - a. A negative history of TB infection and a negative QuantiFERON® TB-Gold In-Tube test and chest x-ray results (see below). QuantiFERON® tests with inconclusive results may be repeated one time. If the repeat result is also inconclusive, the subject will be excluded from the study.

OR,

- b. Subjects with a history of **latent** TB treated with a full course of prophylaxis as per local guidelines, are allowed per investigator judgment. It is the responsibility of the investigator to verify the adequacy of previous treatment and to provide appropriate documentation. *In these cases, no QuantiFERON® test need be obtained.* In addition, must be approved by the medical monitor prior to enrollment. (Any new diagnosis of latent TB or prior untreated/ partially treated latent TB is NOT allowed [ie, subjects who require prophylactic therapy for TB during the study]. Any prior history of active TB [regardless of treatment] is exclusionary.
- 10) A negative chest x-ray (views per local guidelines) for active TB or other lung disease at Screening; or a chest x-ray within 90 days of Screening if films or report are available for investigator review
- 11) A negative pregnancy test is required for female subjects of childbearing potential (as defined per protocol), at Screening and at Day 1, prior to dosing of study drug. Female subjects must agree not to become pregnant for 30 days after the last dose of GS-5745
- 12) Subjects of child-bearing potential (as defined in protocol) must agree to use protocol specified contraceptive measures throughout the study and for 30 days after their last dose of study drug. Female subjects must agree not to become pregnant for 30 days after the last dose of study drug. Male and female subjects taking methotrexate or other drugs should also follow contraception guidelines in the relevant product local label (see [Appendix 5](#))

13) Lactating females must agree to discontinue breastfeeding prior to dosing of study drug and for the duration of the study.

4.3. **Exclusion Criteria**

Subjects who meet *any* of the following exclusion criteria are not to be enrolled in this study.

- 1) Current treatment with any disease modifying anti-rheumatic drug (DMARD) other than MTX, chloroquine or hydroxychloroquine, or current treatment with other immune modulating/suppressive non-biologic and biologic medications as described in Section 5.4.4
- 2) Intra-articular corticosteroid injection within 4 weeks of Baseline
- 3) Any infection requiring oral antimicrobial therapy within 2 weeks prior to Baseline.
- 4) Previous treatment with GS-5745; known hypersensitivity to GS-5745 or its formulation excipients.
- 5) Known hypersensitivity to the TNF inhibitor or its formulation excipients that the subject is receiving at Screening
- 6) Any live or attenuated vaccines within 4 weeks prior to the first dose of study drug or plan to be vaccinated with these vaccines at any time during the study or within 12 weeks after the last dose of study drug.
- 7) Current inflammatory joint disease, other than RA, such as gout, reactive arthritis, psoriatic arthritis, seronegative spondylarthritis, or Lyme disease, **OR** other current autoimmune diseases such as: systemic lupus erythematosus (SLE), inflammatory bowel disease, fibromyalgia, polymyalgia rheumatica, scleroderma, inflammatory myopathy, mixed connective tissue disease, or other overlap syndrome that would interfere with the evaluation of RA or require protocol prohibited medication; (subjects with Sjogren's syndrome or controlled thyroiditis as defined by the investigator are not excluded)
- 8) Active systemic involvement secondary to RA such as vasculitis or Felty's syndrome
- 9) History of any of the following within 12 months of Baseline:
 - a) infection requiring parenteral antibiotics or hospitalization,
 - b) any life-threatening infection,
 - c) sepsis
- 10) History of infected prosthetic joint at any time, with the prosthesis still in situ
- 11) Significant blood loss (>450 mL) or transfusion of blood product within 12 weeks prior to Day 1.

12) Tests performed at the central laboratory at Screening that meet any of the criteria below (out of range lab values may be rechecked one time, after consultation with the sponsor or its designee, before subject is considered a screen-failure):

- a) Hemoglobin <8.0 g/dL (International System of Units [SI]: <80 g/L);
- b) White blood cells <3.0 x 10³ cells/mm³ (SI: <3.0 x 10⁹ cells/L);
- c) Neutrophils <1.5 x 10³ cells/mm³ (SI: <1.5 x 10⁹ cells/L);
- d) Lymphocytes <0.5 x 10³ cells/mm³ (SI: <0.5 x 10⁹ cells/L);
- e) Platelets <100 x 10³ cells/mm³ (SI: <100 x 10⁹ cells/L);
- f) Alanine aminotransferase (ALT) or aspartate aminotransferase (AST) \geq 2.0x ULN;
- g) Total bilirubin level \geq 2x ULN unless the subject has been diagnosed with Gilbert's disease and this is clearly documented;
- h) Estimated glomerular filtration rate <40 mL/min/1.73m² based on the Modification of Diet in Renal Disease (MDRD) formula (See [Appendix 10](#)).
- i) Positive HIV serology during screening
- j) Evidence of active Hepatitis B Virus (HBV) infection. Subjects with positive HBV surface antigen (HBsAg) at screening are excluded from the study. Subjects with negative HBsAg who have positive HBV core Ab, require reflex testing for HBV DNA. Subjects with positive HBV core Ab, and negative HBV DNA at screening will be excluded. Subjects with positive HBV core Ab, and negative HBV DNA are eligible for study entry, per investigator judgment, but may require prophylactic treatment in accordance with HBV treatment guidelines/local standard of care, and require ongoing monitoring with blood tests for HBV DNA every 3 months, as outlined in the schedule of assessments. Subjects with evidence of active Hepatitis B during the study, as evidenced by DNA positivity, will be discontinued from the study drug as outlined in the protocol (Section [3.5.2](#)).
- k) Evidence of active Hepatitis C Virus (HCV) infection. Subjects with a positive HCV Ab at Screening require reflex testing for HCV RNA. Subjects with a positive Hep C RNA at Screening will be excluded. Subjects with a positive HCV Ab, but a negative HCV RNA are eligible, per investigator judgment, but require ongoing HCV RNA monitoring every 3 months. Subjects with evidence of active Hepatitis C during the study, as evidenced by RNA positivity, will be discontinued from the study drug as outlined in the protocol (Section [3.5.2](#)).

13) Any uncontrolled clinically significant laboratory abnormality that would affect interpretation of study data or the subject's participation in the study, per judgment of investigator

- 14) Current malignancy, or a history of malignancy or lymphoproliferative disorder within 10 years of Screening, except:
 - a) Carcinoma in situ of the cervix that has been successfully treated
 - b) Basal or squamous cell cancer or other localized non-melanoma skin cancer that has been successfully treated
- 15) Participation in another investigational drug study within 1 month of Screening (for a small molecule) or within 3 months or 5 drug half-lives prior to Screening, whichever is longer (for a biologic agent)
- 16) Male subjects who are unwilling to refrain from sperm donation during the study and for 90 days after their last dose of study drug
- 17) Female subjects who are unwilling to refrain from egg donation or egg harvesting (for the purpose of current or future fertilization) during the course of the study for 30 days after their last dose of study drug and
- 18) Presence of any condition that could, in the opinion of the investigator, compromise the subject's ability to participate in the study, eg, substance abuse, alcoholism, or an unstable psychiatric condition.
- 19) Known hypersensitivity to rubber or latex
- 20) Have undergone surgical treatments for RA including synovectomy or arthroplasty within the last 12 weeks prior to Screening or planned such surgery during the study
- 21) History of or current moderate to severe congestive heart failure (New York Heart Association [NYHA] class III or IV), or within the last 6 months, a cerebrovascular accident, myocardial infarction, unstable angina, unstable arrhythmia, or a new or significant ECG finding at Screening, or any other cardiovascular condition which, in the opinion of the investigator, would put the subject at risk by participating in the study.
- 22) Any chronic, uncontrolled medical condition which would put the subject at increased risk during the study, such as uncontrolled: diabetes, hypertension, morbid obesity, thyroid, adrenal, pulmonary, hepatic, renal, neurologic or psychiatric disease, or other disease of concern, as per judgment of the investigator.

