 - a) Carcinoma in situ of the cervix that has been successfully treated
 - b) Adequately treated basal or squamous cell cancer that has been successfully treated

Study Procedures/
Frequency:

All subjects will have the following visits at the study site during the blinded period of the study: Screening, Day 1 (first dose of study drug) and Weeks 1, 4, 8 and 12. Subjects will receive the first two injections of study drug (Day 1 and Week 1) at the study site. After completion of the 12 week blinded period of the study, subjects will have the option to participate in the OLE in the same protocol. Subjects who do not participate in the OLE will complete Week 12 assessments and will not receive open label study drug. These subjects

will have a follow up visit 30 days after their last dose of study drug.

Subjects who are eligible will receive their first dose of OLE study drug at Week 12, after completing all the required assessments of the Week 12 visit. Additional OLE study visits will occur at Weeks 13, 19, 24, 30, 36, 42, 48, 54, 60, and 64, with a follow-up visit 30 days after the subject's last dose of study drug.

Screening Assessments

- Confirmation of RA diagnosis
- Medical/Surgical history
- Vital signs to include blood pressure, pulse, temperature and respiration
- Complete physical exam (CPE) height and weight
- 12 lead ECG
- Central laboratory tests including Rheumatoid Factor, anti-CCP, complete blood count, hematology, chemistry panel, urinalysis, urine drug screen, serum β -HCG (women of childbearing potential), QuantiFERON® TB-Gold In-Tube test, HIV, Hepatitis B and C testing (with reflex testing if positive for antibodies), CRP, Estimated Glomerular Filtration Rate (based on MDRD study equation), TSH and HbA1c. Flow cytometry for absolute CD19+ B-cell counts (subjects who have taken rituximab or any B cell depleting agent)
- A negative chest X-ray (views per local guidelines) for active lung disease at Screening; or a chest X-ray within 90 days of Screening if films and/or report are available for investigator review.
- 66 swollen and 68 tender joint counts
- Patient's and Physician's Global Assessment of Health
- Patient's Assessment of Pain

On-Treatment Assessments

- Concomitant medications
- Vital signs to include blood pressure, pulse, temperature, respiration, and weight
- CPE (Blinded period Week 12 and Week 64 only); targeted Physical exam (TPE) at all other visits
- 12-lead ECG (Week 12 blinded period and Week 64 only)

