5.4.4. Disallowed (Prohibited) Concomitant Medications

The disallowed **DMARDs, Biologic Response Modifiers and Other Medications** below require a drug-specific washout period prior to dosing of study drug as defined below. These medications are also not allowed at any time during the 12 week blinded period of the study or during the OLE period, unless otherwise specified:

Synthetic DMARDs

- **Minocycline/doxycycline, penicillamine, and sulfasalazine:** Discontinued for 4 weeks prior to the first dose of study drug.
- **Leflunomide** (Arava®): Discontinued 12 weeks prior to the first dose of study drug or 4 weeks prior to first dose of study drug, if an appropriate washout method has been utilized (either cholestyramine or activated charcoal).
- **Auranofin** (Ridaura®), injectable gold (aurothiglucose or aurothiomalate) or equivalent: Discontinued for 4 weeks prior to the first dose of study drug.
- **Tofacitinib** (Jeljanz®), a Janus kinase inhibitor (Jak inhibitor): Discontinued for 4 weeks prior to the first dose of study drug. Any other JAK inhibitor should also have been discontinued for 4 weeks prior to the first dose of study drug.

Biologic Response Modifiers (Biologic DMARDs)

All of the following are to have been discontinued prior to entry into this study and are prohibited while the subject is receiving study drug:

- **All TNF inhibitors except the TNF inhibitor being administered during Screening:** Discontinued for 12 weeks prior to the first dose of study drug.
- **Abatacept** (Orencia®), **anakinra** (Kineret®), **tocilizumab** (Actemra®): Discontinued for 12 weeks prior to the first dose of study drug.
- **Rituximab** (Rituxan®) or other selective B lymphocyte depleting agents (either marketed or investigational): Discontinued for 6 months prior to the first dose of study drug. Must have normal B cell count as per I/E criteria (see Section 4.2).
- **Other bDMARDs** (including investigational drugs): Should be discussed with the Sponsor.

Other Medications

- **Intramuscular or intravenous corticosteroids:** None should be administered within 30 days prior to the first dose of study drug, or during the blinded part of the study. However, in the OLE, these medications may be used as judged medically necessary by the study investigator.
- **Intra-articular injections:** None should be administered during the blinded part of the study, except for special circumstances (see Section [5.4.2](#)).

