6.2. Pretreatment Assessments

6.2.1. Screening Visit (Day -35 to Day 1)

Written informed consent must be obtained from each subject before initiation of any visit procedures. After a subject has provided informed consent, the investigator will determine if the subject is eligible for participation in the study. Subjects will be screened within 35 days before randomization to determine eligibility for participation in the study. The assessment will include a review of the Inclusion/Exclusion criteria and completion of all Screening Visit procedures as outlined in [Appendix 2](#).

Subjects who do not meet the eligibility criteria will be excluded from randomization and may be considered for rescreening one time for the study in consultation with the Sponsor or its designee

Screening Assessments will include confirmation of RA diagnosis; medical /surgical history; vital signs (VS) to include blood pressure, pulse, respirations, temperature, and weight; height; complete physical exam (CPE); 12 lead ECG; and central laboratory tests including Rheumatoid Factor, anti-CCP, hematology, urinalysis, urine drug screen, chemistry panel, serum β -HCG (women of childbearing potential), QuantiFERON –Gold (QFT), HIV Serology, Hepatitis B and C serologies (if positive reflex testing for positive HBV DNA and HCV RNA), CRP, Estimated Glomerular Filtration Rate (based on MDRD study equation), TSH and HbA1c and flow cytometry for subjects who have been on rituximab. Also included are 66 swollen and 68 tender joint count assessment, Patient's and Physician's Global Health Assessment, and Patient's Assessment of Pain.

A chest x-ray if one has not been performed within 90 days of Screening and films or report available for investigator review

RA disease activity will be determined by DAS28(CRP) at Screening for inclusion criteria and for randomization stratification purposes on Day 1.

Subjects meeting all of the inclusion criteria and none of the exclusion criteria will return to the clinic within 35 days after start of screening for randomization into the study.

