6.2.2. Baseline/Randomization Assessments (Day 1)

Subjects who met the eligibility criteria will undergo the evaluations listed in [Appendix 2](#).

Day 1 evaluations will include the following: Review of AEs and concomitant medications, vital signs, targeted physical exam, urine pregnancy test, clinical laboratory examinations (hematology, urinalysis, chemistry panel, hsCRP, and Erythrocyte Sedimentation Rate [ESR]; performed locally using the Westergren method), and anti-drug antibodies (ADA) blood draw, biomarker blood draws, study drug administration, tender and swollen joint counts, patient global assessment of pain, physician assessment of global disease activity, patient global assessment of disease activity, SF-36, Health Assessment Questionnaire (HAD-QI), and optional collection of blood for DNA analysis (genomic testing).

All Day 1 procedures and assessments should be completed prior to randomization and study drug administration.

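### Inclusion criterion 7 accepts 8 weeks off tocilizumab or infliximab, while Protocol Section 5.4.4 requires 12 weeks

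*Protocol*

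**What the plan says.** Protocol Section 4.2, inclusion criterion 7, declares subjects with earlier biologic DMARD treatment eligible provided that drug-specific washouts have been met. Two of the three entries are "Infliximab – none for at least 8 weeks prior to Baseline" and "Tocilizumab – none for at least 8 weeks prior to Baseline". The third, rituximab, is 6 months plus a normal CD19+ B-cell count.

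Protocol Section 5.4.4 sets its own washouts for biologics and says that the listed drugs must have been stopped before study entry. The entry covering abatacept, anakinra and tocilizumab ends "Actemra®): Discontinued for 12 weeks prior to the first dose of study drug". The same 12 weeks apply to "All TNF inhibitors except the TNF inhibitor being administered during Screening". Rituximab is again 6 months, with a reference back to Section 4.2 for the B-cell count.

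The one link from the exclusion criteria to these washouts is exclusion criterion 1 in Section 4.3. On this point it excludes "current treatment with other immune modulating/suppressive non-biologic and biologic medications as described in Section 5.4.4".

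**The concern.** The protocol gives two minimum washouts for the same drugs, and both decide who may enter. Criterion 7 states positively that a subject 8 weeks off either drug is eligible; Section 5.4.4 bars that subject until 12 weeks. Exclusion criterion 1 does not settle the matter, because it points to Section 5.4.4 only for treatment that is current, and a drug stopped 8 weeks ago is not.

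Section 6.2.1 sends subjects on to randomization by the eligibility lists alone: "Subjects meeting all of the inclusion criteria and none of the exclusion criteria will return to the clinic within 35 days". A site that follows those lists faithfully could randomize a subject whom another section excludes, and would have no reason to record a deviation.

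What is at stake is a single consistent eligibility and safety washout. Protocol Section 1.4 notes that combining TNF inhibitors with other biologics acting directly on the immune system raised the risk of serious infection. It names limits on immune-modulating agents among the trial's precautions. The documents give no reason for choosing either 8 or 12 weeks.

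**Working it through.** The plan states no figure to reproduce. The check puts the two rules on one calendar and subtracts.

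**1. Common reference day.** Criterion 7 counts back from Baseline, and Section 5.4.4 counts back from first dose. The heading of Section 6.2.2 places Baseline on Day 1 ("Baseline/Randomization Assessments (Day 1"). The visit list in the Synopsis makes Day 1 the first-dose day ("Screening, Day 1 (first dose of study drug) and Weeks 1, 4, 8 and 12"). Both periods therefore end on the same day.

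**2. The rules side by side.**

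| Prior drug | Section 4.2, criterion 7 | Section 5.4.4 | Agree? |
|---|---|---|---|
| Tocilizumab | 8 weeks = 56 days | 12 weeks = 84 days (named) | No |
| Infliximab | 8 weeks = 56 days | 12 weeks = 84 days (as a TNF inhibitor) | No |
| Rituximab | 6 months | 6 months | Yes |

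The rituximab row, with its cross-reference, suggests that the two sections were meant to match.

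**3. Can infliximab fall under the exception for the current TNF inhibitor?** No. Criterion 6 requires the ongoing agent to be subcutaneous and lists adalimumab, certolizumab, etanercept, golimumab or a marketed biosimilar. Infliximab is not among the named agents, and criterion 7 treats it as a previous drug.

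**4. Width of the conflict.** Criterion 7 is met when the last dose was at least 56 days before Day 1. Section 5.4.4 is not met when it was fewer than 84 days before. The conflict covers days 56 to 83, that is 84 − 56 = 28 days.

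**5. Who can be in the gap.** Criterion 6 also requires at least 12 weeks (84 days) of the ongoing TNF inhibitor. The minimum time from starting that drug to the last dose of the earlier one depends on where those 84 days are counted:

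- Counted to Day 1: from 84 − 83 = 1 day to 84 − 56 = 28 days.
- Counted at a Screening visit 35 days before Day 1, as the target population in the Synopsis suggests: the start is at least 84 + 35 = 119 days before Day 1, giving 119 − 83 = 36 days to 119 − 56 = 63 days.

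Either way, a subject in the gap took the earlier biologic after starting the current TNF inhibitor. That must be rare, but neither section rules it out.

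**6. Would the reported outputs show it?** SAP Section 4.3 lists subjects who failed an inclusion or exclusion criterion; this subject meets criterion 7. SAP Section 7.4 provides no summary or listing of prior medications.

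**The case against.** The strongest reply is that both rules are minimums, so a site following the whole protocol applies 12 weeks and breaches neither. Section 9.1.9 does require conduct according to the whole protocol. This is why 12 weeks is the safe harmonization, but it does not cure criterion 7, which declares the subject eligible at 8 weeks.

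Second, criterion 6 leaves the difference with almost no practical effect. That stands, and it limits the importance of the point.

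Third, Section 5.4.4 does not name infliximab, and the named entry in criterion 7 might be read as a specific rule overriding a general one. The infliximab part does rest on its drug class, which the documents do not state. The tocilizumab part needs no inference.

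Fourth, the SAP supports only a synoptic report after the sponsor stopped the study with 15 subjects enrolled, so its short list of outputs says little about what a full trial would have reported. The protocol also requires sites to document deviations (Section 6) and keep eligibility and medication records (Section 9.1.5), and monitors to verify adherence (Section 9.3.2). This weakens the argument from the SAP. A site relying on criterion 7 could still fail to recognize a deviation.

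**Conclusion.** The inconsistency is real. For tocilizumab it is explicit; for infliximab it follows from its being a TNF inhibitor. The two sections disagree by 4 weeks, affecting last doses 56 to 83 days before Day 1, and no text gives either section precedence. Very few subjects could fall in that interval, and the documents do not allow a count. Sample size, power, type I error and the treatment comparison are unaffected, and the SAP plans no inferential analysis. The point merits correction because an eligibility threshold admits subjects whom another section bars. It is not a threat to the primary result.

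**What to change.** In Protocol Section 4.2, criterion 7, change the infliximab and tocilizumab entries from 8 to 12 weeks before first dose, or replace them with a reference to Section 5.4.4. Apply the same 12 weeks in the eligibility check. The sponsor's intended interval is not documented, but 12 weeks meets both sections as they stand.

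The cost is one wording change and one check on the eligibility form. Recruitment loss would be close to nil, because criterion 6 already leaves very few subjects in the gap. For the 15 subjects already enrolled, checking the stop dates of earlier biologics against the 56-to-83-day interval would show whether anyone was affected.
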